6.4 Description of Study Assessments/Investigations

6.4.1 Demographics and Medical History

The Investigator will collect and report in the eCRF demographics and complete history of malignant and clinically-significant non-malignant diseases including known hypersensitivity reactions.

6.4.2 Physical Examination and Vital Signs

At screening physical examinations will include a complete assessment of body systems (i.e. general appearance, head, eyes, ears, nose, mouth, skin, heart, lungs, lymph nodes, gastrointestinal, genitourinary, skeletal, and neurologic) per standard of care at the study site or as clinically indicated by symptoms. Weight will also be measured at screening.

During treatment period visits and at the End of Treatment visit, a symptom-directed physical examination will be done.

Vital signs will be assessed as per site's standard practice.

6.4.3 ECOG Performance Status

Assessment of ECOG PS (Appendix 1) is required to assess subject's functional status for study eligibility purposes and will be performed throughout the study according to the Schedule of Visits and Assessments (section 6.2).

6.4.4 Adverse Events Assessment and Concomitant Treatments Review

- Adverse events assessment: For information on the assessment and collection of AEs refer to section 7 and to the Schedule of Visits and Assessments in section 6.2.
- Concomitant Treatments: Concomitant treatment includes any medication or therapeutic procedure (e.g. prescription drugs, over-the-counter drugs, herbal/homeopathic remedies, nutritional supplements, blood transfusions, etc.) used by a subject from the date the PICF is signed until the End of Treatment visit. After the End of Treatment visit, in Part A, only concomitant therapies to treat AEs related to study treatment and any SAE (regardless of the relationship) will be recorded. In Part B only concomitant treatments to treat AEs/SAEs related to study treatment will be collected after the End of Treatment visit.

6.4.5 Laboratory Safety Assessments

The following laboratory safety assessments will be done according to the Schedule of Visits and Assessments in section 6.2.

- Hematology: hemoglobin, Absolute Neutrophils Count (ANC) and platelets
- Blood chemistry: AST, ALT, Alkaline Phosphatase, Total Bilirubin, Creatinine, Glucose, TSH
- Coagulation tests: INR or PT and aPTT/PTT
- Serum pregnancy test: only in women of childbearing potential

6.4.6 Efficacy Assessments

Efficacy assessments include:

- Evaluation of tumor burden according to the irRECIST to assess irPFS, irORR, irDOR and irDCR
- Serial measurement of CA-125 to monitor for response according to the GCIG criteria in subjects with CA-125 evaluable disease at baseline

6.4.6.1 Schedule/Details of Tumor Burden Assessments

All efficacy endpoints (including the primary and secondary objectives in both Part A and B) are linked to the tumor burden response assessments and therefore the importance of timely and complete disease assessments in this study cannot be understated. Failure to perform any of the required disease assessments will result in the inability to determine disease status for that time point. Frequent off schedule or incomplete disease assessments have the potential to weaken the conclusion of this clinical trial.

The schedule of tumor burden assessments should be fixed according to the calendar, regardless of treatment interruptions. Tumor burden assessments will be performed until progressive disease as per irRECIST regardless of the discontinuation of study treatment, the start of a subsequent anticancer therapy or CA-125 values.

The same method of assessment and the same technique used at baseline (CT scan or MRI) to characterize each lesion must be used at each subsequent post-baseline assessment. Review of post-baseline scans and assessment of overall response (according to irRECIST) should be done at the next visit after the scans are performed and prior to indicating subsequent study therapy, to rule out progressive disease that would warrant study treatment discontinuation.

The irRECIST guidelines for measurable, non-measurable, target and non-target and the tumor response criteria are presented in Appendix 2.

6.4.6.1.1 Baseline assessments

Baseline disease assessments should be performed as close as possible to the treatment start and never more than 28 days before enrollment in Part A or randomization in Part B. Disease assessment at screening will be used to determine the measurability of the disease (measurable versus non-measurable) and to document lesions as Target or Non-Target lesions as per irRECIST. Subjects without measurable lesions are not eligible in Part A. Subjects who have no measurable and no non-measurable lesions are not eligible in Part B (i.e. subjects categorized as “No Disease” (irND) according to irRECIST).

Baseline assessment will include at least:

- CT or MRI scan of the chest, abdomen, and pelvis (CAP)
- Any additional imaging as deemed appropriate
- If applicable, clinical assessment of superficial lesions

6.4.6.1.2 Post-baseline assessments

Post-baseline assessments will be done:

- In Part A:
 - 6 weeks (\pm 1 week) after first CC-486 intake (first post-baseline tumor assessment).
 - Thereafter, every 12 weeks (\pm 1 week), always taking as a reference the date of the first post-baseline tumor assessment (not the date of the immediately previous tumor assessment).
 - Whenever disease progression is suspected based on signs, symptoms, performance status deterioration, CA-125, etc.
 - Confirmation of progression (irPD) is recommended minimum 4 weeks after the first irPD assessment and is required during the flare time-window of the first 12 weeks of treatment.
- In Part B:
 - Every 12 weeks (\pm 1 week), always taking as a reference the date of randomization in the study (not the date of the immediately previous tumor assessment)
 - Whenever disease progression is suspected based on signs, symptoms, performance status deterioration, CA-125, etc.
 - Confirmation of progression (irPD) is recommended minimum 4 weeks after the first irPD assessment and is required during the flare time-window of the first 12 weeks of treatment.

Post baseline assessments will include at least:

- CT or MRI scan of the chest, abdomen, and pelvis (CAP)
- Any other imaging that revealed lesions at baseline
- Any additional imaging as deemed appropriate

6.4.6.2 CA-125 Measurements

CA-125 will be measured in all subjects at baseline, at each pre-treatment visit during the study treatment phase and at the End of Treatment visit. During follow-up, CA-125 will be tested only in subjects without irPD at time of treatment discontinuation and until irPD is declared. CA-125 measurement is not required following irPD. Whenever possible, CA-125 should be tested at the same laboratory and with the same technique throughout the study.

CA-125 will be used to assess tumor response based on the GCIG criteria but will not be used to declare disease progression and/or study treatment discontinuation. Any elevation in CA-125 suggestive of disease progression needs to be confirmed through tumor burden disease assessments as an irPD to declare progression and to warrant study treatment discontinuation. CA-125 elevation alone is not defined as disease progression. If the elevation of CA-125 is not radiographically confirmed as an irPD, study treatment should continue until progression based on irRECIST, unless the Investigator concludes that it is in the best interest of the subjects to discontinue protocol therapy.

6.4.6.2.1 Evaluation of Response according to CA-125

The GCIG has developed criteria for defining response and progression of ovarian carcinoma based on CA-125.²⁴ The GCIG recommends that for trials of relapsed ovarian cancer the following definition for response according to CA-125 be used.

Definition of response: A response according to CA-125 has occurred if there is at least a 50% reduction in CA-125 levels from a pre-treatment sample. The response must be confirmed and maintained for at least 28 days. Subjects can be evaluated according to CA-125 only if they have a pre-treatment sample that is at least twice the upper limit of normal and within 2 weeks prior to starting treatment (TRIO026 study requires that baseline CA-125 is tested within 7 days prior to enrollment in Part A or randomization in Part B).

To calculate CA-125 responses accurately, the following rules apply:

- Intervening samples and the 28-day confirmatory sample must be less than or equal to (within an assay variability of 10%) the previous sample.
- Variations within the normal range of CA-125 levels will not interfere with the response definition.
- For each subject, it is preferred that the same assay method be used, and the assay must be tested in a quality-control scheme.
- Subjects are not evaluable by CA-125 if they have received mouse antibodies (unless the assay used has been shown not to be influenced by Human anti-mouse antibody) or if there has been medical and/or surgical interference with their peritoneum or pleura during the previous 28 days.

The date when the CA-125 level is first reduced by 50% is the date of the CA-125 response.

6.4.7 Biological Sampling Procedures

The area of research into the identification of tumor markers and biological processes / targets to aid in the identification of clinical benefit in certain subsets of populations or even in the identification of anticancer therapies to target the marker, is rapidly growing. Tumor samples will be used to assess

potential prognostic or predictive markers, improve understanding of ovarian cancer biology and identify candidate biomarkers that may correlate with treatment benefit and/or safety signals.

As more development and information is revealed in the future, TRIO would like to use these tumor samples for measurement of the new markers. The tumor samples will be stored in the TRIO central laboratory until future use is required. TRIO may collaborate in the future with experts in the field, and the tumor material may be shared with other researchers.

Details on the analyses to be performed on the biologic samples and procedures for sample collection, labeling, storage and shipment/return of biological samples will be described in separate document(s) (e.g. Samples Manual, Samples Plan).

All samples will be submitted to central laboratories (located in the USA) and will be stored for an indefinite time period unless otherwise required by the subject, Investigator, ethics committee and/or regulations.

Refer to the Schedule of Visits and Assessments in section 6.2 for the samples collection time points.

6.4.7.1 Tumor core biopsies: Fresh-frozen tissue (FFT) and Formalin-fixed paraffin-embedded (FFPE) samples

These samples are mandatory in Part A and optional in Part B.

In all subjects participating in Part A, tumor samples will be collected through image-guided core biopsy at baseline and 6 weeks (± 1 week) after first CC-486 intake (provided that the tumor lesion is amenable to a second biopsy). The second biopsy must be done during the on-treatment period of the second CC-486 cycle. As much as possible and if clinically indicated, the second biopsy should be scheduled to coincide with the 1st post-baseline tumor burden assessment (both 6 weeks ± 1 week after first CC-486 intake) so the image-guided biopsy is done at the same time the subject undergoes the scans to assess response/progression.

In Part B, tumor will be collected in the same time points and with the same procedure as in Part A, in subjects consenting to participate in this optional tissue acquisition study, provided they have lesion(s) amenable to biopsy.

A minimum of three cores at each time point is required to perform the molecular analyses. If three cores are taken, two of them will be formalin-fixed paraffin-embedded and one will be fresh-frozen. If a different number of cores is taken, (approximately) half of them will be fresh-frozen and the other half formalin-fixed paraffin-embedded. If only one core can be obtained, this only core will be fresh-frozen.

Once the cores have been removed, the applicable number of cores must be immediately snap-frozen (procedure described in the study Laboratory Manual), while the remaining ones will be formalin-fixed according to site's procedures.

Both in Parts A and B, if feasible, a fresh-frozen ascites sample will also be collected in subjects with ascites, during the same procedure as the biopsy.

All these samples will be transported to the Translational Oncology Research Labs at the University of California, Los Angeles (TORL-UCLA).

6.4.7.2 Formalin-Fixed Paraffin-Embedded (FFPE) block/partial block from the debulking surgery

For Part A and Part B subjects consenting to this optional tissue acquisition part of the study, a FFPE block/partial block from the EOC debulking surgery will be obtained and submitted to the TORL-UCLA.

FFPE tumor tissue will be used for biomarker research. In case FFPE tissue block cannot be provided, a minimum of 15 unstained slides would be required to be submitted to the TORL-UCLA.

6.4.7.3 Whole-blood samples for DNA methylation analysis

These samples are mandatory in Part A and will be used to analyze changes in DNA methylation during treatment with CC-486. Peripheral whole blood samples will be obtained on Day 1 of the 1st CC-486 cycle (prior to the first CC-486 intake) and on the pre-treatment visit prior to the 2nd CC-486 cycle.

6.5 Subject Discontinuation

The Investigator has the right to discontinue a subject from study treatment or withdraw a subject from the study at any time. In addition, subjects have the right to voluntarily discontinue study treatment or withdraw from the study at any time for any reason.

6.5.1 Discontinuation from Study Treatment

Refer to section 5.5.

6.5.2 Discontinuation from Study Participation

The primary reason for study participation discontinuation should be documented on the eCRF. Reasons for subject's discontinuation from the study include:

- Death
- Consent withdrawal from entire study participation
- Subject completes the follow-up period as per protocol sections 6.3.3 and 6.3.4
- Subject non-compliance
- Lost to follow-up

Should a subject decide to withdraw consent, all efforts will be made to complete and report the observations as thoroughly as possible. The Investigator should contact the subject by telephone or through a personal visit to establish as completely as possible the reason for the withdrawal. A complete final evaluation at the time of the subject's withdrawal should be made with an explanation of why the subject is withdrawing from the study. After complete withdrawal of consent, no further study procedure will be performed and no further data will be collected after the date of the subject's withdrawal from study.

Partial withdrawal occurs when the subject withdraws consent but agrees to be contacted for further information on survival. It should be documented in both the medical records and the eCRF that the subject agreed to be contacted for information on survival despite the subject's withdrawal of informed consent. Partial consent withdrawal is not considered a discontinuation from study participation.

In the case a subject does not show up for study visits, site staff should make reasonable contact attempts before declaring the subject as lost to follow-up. These attempts need to be documented in the medical records.

7. SAFETY MONITORING

7.1 Definitions

7.1.1 Period of Observation

At each visit and any contact during the study and follow-up period, the Investigator or designee will inquire about the occurrence of AEs and will document them in the subject file.

The Investigator or designee will report the AEs in the eCRF and to TRIO Drug Safety and Pharmacovigilance Department when required as per the table below:

Table 8: Reporting period of AEs/SAEs

Study period	AEs (non-serious)		Serious Adverse Events/Pembrolizumab Events of Clinical Interest (ECI)	
	Part A	Part B	Part A	Part B
From PICF to first dose	Not required to report	Only if related to study participation	Only if related to study participation	Only if related to study participation
Study treatment period until End of Treatment visit	All (regardless of relationship)	All (regardless of relationship)	All (regardless of relationship)	All (regardless of relationship)
From End of Treatment visit until End of subject participation ¹	Only if related to study treatment	Only if related to study treatment)	All (regardless of relationship)	Only if related to study treatment

¹ The applicable events as per the table that are ongoing at time of the End of Treatment visit should be followed up to resolution or until the event becomes stable (or returns to baseline) or is unlikely to resolve further in the opinion of the Investigator. Regarding SAEs, in Part A all should be reported/ followed after the End of Treatment visit, regardless of the relationship with the study drugs. In Part B, only study-drug related SAEs should be followed/ reported.

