Subjects will be treated in the assigned cohort until progressive disease based on irRECIST, unacceptable toxicity, consent withdrawal or the Investigator concludes that it is in the subject's best interest to discontinue (or any other withdrawal criteria is met according to section 5.5). Subjects who discontinue treatment for reasons different than irPD will enter the follow-up phase and will continue to be followed with tumor assessment every 12 weeks until irPD. After irPD, and provided that subject has undergone the End of Treatment visit, all subjects will be taken off the study unless presence of serious adverse events (SAEs) or study treatment-related adverse events. In such case these events will be monitored as clinically indicated until the events have resolved (or return to baseline) or in the Investigator's opinion, are unlikely to resolve due to the nature of the condition and/or the subject's underlying disease.

Once 5 subjects in each cohort are considered evaluable, enrollment will be stopped and data from each cohort will be analyzed and the optimal schedule to be taken forward into Part B will be selected according to section 3.3.

Part A includes mandatory tumor core biopsies for biomarkers research and mandatory whole blood sampling for DNA methylation analyses (see section 6.4.7).

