12: CT/MRI of chest abdomen and pelvis to be done at each tumor assessment. The schedule of assessments should be fixed according to the calendar, regardless of treatment interruptions. The first post-baseline assessment will be done 6 weeks (\pm 1 week) after first CC-486 intake. Subsequent assessments should be done thereafter every 12 weeks (\pm 1 week) taking as a reference the date of the first post-baseline tumor assessment. Tumor burden assessments will be done according to irRECIST criteria until documentation of irPD regardless of the end of study treatment and start of subsequent anticancer therapy or CA-125 values. Confirmation of progression (irPD) is recommended minimum 4 weeks after the first irPD assessment and is required during the flare time-window of the first 12 weeks of treatment. If there is suspicion of disease progression based on clinical or laboratory findings before the next scheduled assessment, an unscheduled assessment should be performed at the Investigator's discretion. During the follow-up, tumor assessments will only be required in subjects without irPD at time of End of treatment visit.

13: For subjects consenting to this optional tissue acquisition part of the study, a FFPE block/partial block from the EOC debulking surgery will be obtained (or a minimum of 15 unstained slides in case FFPE tissue block cannot be provided).

14: Image-guided core tumor biopsy is mandatory at baseline (within 28 days of study treatment start) and 6 weeks (\pm 1 week) after first CC-486 intake. The second biopsy must be done during the on-treatment period of the 2nd CC-486 cycle. As much as possible and if clinically indicated, the second biopsy should be scheduled to coincide with the 1st post-baseline tumor burden assessment (both 6 weeks \pm 1 week after first CC-486 intake) so the image-guided biopsy is done at the same time the subject undergoes the scans to assess response/progression. If feasible, a fresh-frozen ascites sample will also be collected in subjects with ascites, during the same procedure as the biopsy. Refer to section 6.4.7.1 and the Study Laboratory Manual for additional details.

15: Whole blood for DNA methylation analysis will be obtained via venipuncture. On day 1 of the 1st CC-486 cycle, sample should be obtained prior to the first CC-486 intake.

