12: CT/MRI of chest abdomen and pelvis to be done at each tumor burden assessment. The schedule of assessments should be fixed according to the calendar, regardless of treatment interruptions and taking as a reference the randomization date. Tumor burden assessments will be done according to irRECIST criteria until documentation of irPD regardless of the end of study treatment and start of subsequent anticancer therapy or CA-125 values. Confirmation of progression (irPD) is recommended minimum 4 weeks after the first irPD assessment and is required during the flare time-window of the first 12 weeks of treatment. If there is suspicion of disease progression based on clinical or laboratory findings before the next scheduled assessment, an unscheduled assessment should be performed at the Investigator's discretion. During the follow-up, tumor assessments will only be required in subjects without irPD at time of End of treatment visit and only until irPD.

13: For subjects consenting to this optional tissue acquisition part of the study, a FFPE block/partial block from the EOC debulking surgery will be obtained (or a minimum of 15 unstained slides in case FFPE tissue block cannot be provided).

14: Image-guided core tumor biopsy is an optional procedure and will be collected in consenting subjects with lesion amenable to biopsy, at baseline (within 28 days of study treatment start) and 6 weeks (± 1 week) after first dose of study treatment. If feasible, a fresh-frozen ascites sample will also be collected in subjects with ascites, during the same procedure as the biopsy. Refer to section 6.4.7.1 and the Study Laboratory Manual for additional details.

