3.5.2. Adverse Events (AEs)

AE information will be collected from treatment initiation and continues throughout the study until end of participation (refer to Section 7.1.1 of the protocol).

[figure not shown]
The reported AE term will be coded using the current version of the MedDRA. The severity of AE will be presented as reported by the investigator based on National Cancer Institute Common Terminology Criteria for Adverse Events (NCI CTCAE) grades version 4.03.

Incidence of AEs will be tabulated by SOC and PT for:

- All AEs
- AEs by relationship to study treatment and maximum severity grade
- AEs with action taken drug interrupted
- AEs with action taken dose reduced
- AEs with action taken drug withdrawn
- Serious Adverse Events (SAE)
- AEs leading to deaths – An AE is considered as leading to death if CTCAE Grade 5 is reported.

In the event a patient experiences repeated episodes of the same AE according to PT, the event with the highest severity grade to study treatment will be used for purposes of incidence tabulations.

Detailed listings for all AEs will be provided.

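### Part A, where the baseline research biopsy is mandatory, does not require non-serious events before first dose to be reported, and the SAP's AE and SAE outputs omit pre-dose serious events in never-dosed subjects

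*Protocol*

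**What the plan says.** **Reporting periods (Protocol 7.1.1, Table 8).** From consent to first dose, the Part A cell for non-serious AEs reads "Not required to report". The matching Part B cell reads "Only if related to study participation". Serious events and events of clinical interest in that period carry the Part B wording in both parts. From first dose to the End of Treatment visit, all events are reported in both parts. The same section separates asking from reporting: at every visit the investigator or designee "will inquire about the occurrence of AEs and will document them in the subject file", and Table 8 then decides what goes to the eCRF and the sponsor.

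**The biopsy.** Protocol 3.1 states: "Part A includes mandatory tumor core biopsies for biomarkers research". Table 6, footnote 14, adds: "Image-guided core tumor biopsy is mandatory at baseline (within 28 days of study treatment start". For Part B, Table 7, footnote 14, says: "Image-guided core tumor biopsy is an optional procedure and will be collected in consenting subjects with lesion amenable to biopsy".

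**The analysis.** SAP 3.5.2 states: "AE information will be collected from treatment initiation and continues throughout the study until end of participation", and refers to Protocol 7.1.1. SAP 3.1.2 defines the Safety Population as patients who received any study treatment. SAP 3.5 and the output lists in SAP 5.1 and 5.2 place every AE and SAE table and listing on that population. The Deaths listing is on the ITT Population, which consists of enrolled patients.

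**The concern.** The part of the trial that requires an invasive research procedure of everyone has the weaker rule for reporting its non-serious harms. The documents give no reason for the difference.

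The SAP adds a second gap. Protocol 7.1.1 makes a participation-related serious event reportable from consent, but the SAP section that cites it describes collection only from treatment initiation. The outputs then exclude anyone who was not dosed. At stake is whether the Part A report can describe complications of a procedure that subjects undergo for biomarker research. The choice of CC-486 schedule is not at stake.

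**Working it through.** No figure in the plan bears on this point, so the check is a comparison of sections.

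**Step 1. Where the baseline biopsy falls.** Table 6 places it in screening, Days -28 to -1, with Day -1 the day before enrollment. Protocol 6.1.2.1 puts screening first, then central eligibility review, then enrollment, with treatment starting within 3 days of enrollment. The biopsy is therefore in the consent-to-first-dose row of Table 8, and normally before enrollment.

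**Step 2. Follow each kind of Part A event through both documents.**

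| Event | Protocol reporting duty | SAP output |
|---|---|---|
| Non-serious, after baseline biopsy, subject later dosed | None in Table 8; eCRF entry under section 5.6 if medication is given for it | No clear place, since collection is described from treatment initiation |
| Non-serious, after baseline biopsy, never dosed | As above | None; outside the Safety Population |
| Serious and participation-related, pre-dose, subject later dosed | Reportable | Unclear: in the population, but before the start stated in SAP 3.5.2 |
| Serious and participation-related, enrolled, never dosed | Reportable | No AE or SAE output; a death would appear in the ITT Deaths listing |
| Serious and participation-related, screen failure | Reportable | None; outside both the Safety and ITT Populations |
| Any event after the 6-week biopsy, on treatment | All reported | Included in the AE outputs |

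**Step 3. Compare with Part B.** A non-serious complication of the optional baseline biopsy would be reportable if it counts as related to study participation. The protocol does not define that term, and the Part B SAP is a separate document that is not available, so how Part B would tabulate the event is unknown.

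**Step 4. Check section 5.6.** It counts concomitant treatment from consent and requires an AE that leads to medication to be entered in the eCRF. For a medicated biopsy complication in Part A this points the opposite way from Table 8.

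**Step 5. Size.** SAP 2.3 plans at least 4 × 5 = 20 patients, more with replacements. The documents give no complication rate, so a range of 5 to 15% for non-serious complications is assumed:

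- 20 × 0.05 = 1 event
- 20 × 0.15 = 3 events

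If events were collected and none occurred in 20 subjects, the one-sided 95% upper bound on the rate would be 1 − 0.05^(1/20) = 0.139, about 14%. Under the current Table 8 rule, no such statement can be made for non-serious baseline-biopsy events.

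**The case against.** The case on the other side has substance, and most of it limits the consequences.

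- **Biopsy harm is measured in Part A.** Each evaluable subject has a second core biopsy at about 6 weeks, on treatment, when every AE is reported. A reader might infer that the sponsor would offer the biopsy in Part B without any measurement of its harm. The documents do not support that: at least 20 evaluable subjects contribute full AE reporting around the second biopsy.
- **Serious events reach the sponsor.** A reader might also infer that the Part A report would show no baseline-biopsy harm whatever happened. That goes too far. Participation-related serious events are reportable before dosing, deaths in enrolled subjects are listed on ITT, and medicated events have an eCRF route through section 5.6. The SAP also states no treatment-emergent filter, so a pre-dose serious event in a subject who is later treated is not expressly excluded from the listings.
- **Events are not lost at the site.** They stay in the subject file. The AE assessment at screening in Table 6 and section 6.3.1 can look like a contradiction of Table 8, but Protocol 7.1.1 treats assessment and reporting as separate duties, so the two are compatible.
- **No decision depends on it.** The toxicity criteria in Protocol 3.3 count only AEs related to study drugs.
- **The rule fits the AE definition.** Protocol 7.1.2 defines an AE in a subject who received a pharmaceutical product. That makes the Part A cell defensible taken alone. It does not explain why Part B differs, or why the rule is weaker where the biopsy is compulsory.

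Two things remain standing: the difference between the Part A and Part B cells, and the absence of any AE or SAE output for pre-dose serious events in never-dosed subjects.

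**Conclusion.** The point holds as a limited gap in reporting procedure harms that is cheap to close. In Part A, non-serious events after the mandatory baseline biopsy carry no Table 8 reporting duty, unless section 5.6 brings in those treated with medication. SAP 3.5.2 does not match the pre-dose serious-event reporting in the section it cites, and a reported serious complication in a subject who is never dosed appears in no AE or SAE output.

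The likely size is small: 1 to 3 non-serious events in 20 subjects under the assumed 5 to 15% rate. Even complete collection with no events would only bound the rate at about 14%. The case for change is that subjects undergo the procedure for research and the sponsor already uses the stricter wording in Part B.

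The conclusion assumes that a biopsy complication counts as related to study participation, which is the natural reading but is not defined.

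**What to change.** 1. **Table 8:** change the Part A non-serious cell for consent to first dose to "Only if related to study participation", the wording already used for Part B. The eCRF guidance should say that this covers study-specific screening procedures.
2. **Section 5.6:** reconcile it with Table 8, so that sites know which rule governs a pre-dose event treated with medication.
3. **SAP 3.5.2:** align the stated start of collection with Table 8.
4. **SAP 5.2:** add one listing of AEs and SAEs from consent to first dose that are related to study participation, kept apart from the treatment-period tables. It should cover all consented subjects who had a study procedure, including screen failures. Limiting it to enrolled subjects would miss a subject harmed at screening who is never enrolled.

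The cost is one table cell, two wording alignments, one listing and short eCRF guidance. The downside is a few extra AE entries and limited eCRF collection for screen failures. Design, sample size and schedule selection do not change.
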